6.3.8. Impact of AECOPD on healthcare utilisation

Descriptive statistics of the daily number of healthcare utilisation (number of HCU in the relevant period divided by the number of days) within the stable period and within the exacerbation period will be presented overall and divided by the following unscheduled visits:

1. Number of physician office consultations,
2. Number of visits to urgent care,
3. Number of visits to emergency department,
4. Number of hospitalizations.

Healthcare use for each patient will be obtained through review of the patient's medical record (aided by patient daily self-reporting in the eDiary).

Healthcare utilisation will be summarized according to COPD grade at enrolment, smoking status, sex and age at enrolment. In addition, healthcare utilisation will be summarized by AECOPD severity during exacerbations.

Overall HCU [total number and divided by type of HCU] per patient will be correlated to the number of exacerbation experienced during the observation time.

Current medication for COPD and additional COPD treatments prescribed by primary and secondary care physicians within the stable period and within the exacerbation period will be described by drug category overall and by COPD grade at enrolment, smoking status, sex and age at enrolment. In addition, current medication for COPD and additional COPD treatments prescribed will be summarized by AECOPD severity during exacerbations.

6.4. Analysis of tertiary objective

The analyses of the tertiary objectives will be performed on the full analysis set.

6.4.1. End date of AECOPD using EXACT-PRO

Descriptive statistics (N, mean, median, standard deviation, minimum and maximum, first and third quartiles) on the average length of AECOPD episodes, as estimated with the EXACT-PRO (section 12), will be presented, for any, mild, moderate and severe AECOPD.

Descriptive statistics of the number of patients according to their percentage of days within exacerbation periods out of the total observation period as estimated with the EXACT-PRO will be presented.

The frequency distribution of exacerbation confirmed at site visit or through medical records (with or without morning symptoms diary alert) will be tabulated versus EXACT-PRO exacerbations. The concordance between investigator judgement and EXACT-PRO exacerbations will be evaluated using the Cohen's kappa (κ) test, with 95% CI. Concordance will be interpreted as good (>0.79), substantial (0.60–0.79), moderate (0.40–0.59), or fair (0.21–0.39) or no concordance (<0.21).

Descriptive statistics (N, mean, median, SD, minimum, maximum, first and third quartiles) for the EXACT daily scores will be tabulated at baseline, during the day before exacerbation, at exacerbation onset and at recovery according to investigator judgement. These statistics will be reported overall and for any mild, moderate or severe exacerbation visit.

Graphs detailing the EXACT-PRO scores before during and after exacerbation onset as defined clinically will be also presented.

Difference from baseline, with 95% CI, of EXACT score measured at stable scheduled visit will be plotted.

6.4.2. Mixed infections

The simultaneous bacterial [culture/PCR] and viral presence in sputum at enrolment, any stable and any exacerbation visit [mild, moderate, severe] will be computed overall and by pathogens.

6.4.3. Load of bacteria and virus

Total number of patients providing a sputum sample, the number of sputum samples positive to specific bacteria (by culture) and the frequencies of semi-quantitative bacteriological load (few scattered, +, ++, +++) will be tabulated at each scheduled [stable] visit and at each exacerbation visit.

Total number of patients providing a sputum sample, the number of sputum sample positive to specific bacteria (by PCR)/virus and average load will be tabulated at each scheduled [stable] visit and at each exacerbation visit.

6.4.4. Impact of occurrence of bacterial/viral pathogens in sputum on AECOPD

The following proportions will be computed:

- Proportion of patients with sputum samples which are positive for specific pathogens [NTHi, Mcat, *S. pneumoniae*, HRV] during an AECOPD visit but not in the previous stable visit/in the previous visit
- Proportion of patients with sputum samples which are negative for specific pathogens [NTHi, Mcat, *S. pneumoniae*, HRV] during an AECOPD visit but not in the previous stable visit/in the previous visit
- Proportion of patients with sputum samples which are positive for specific pathogens [NTHi, Mcat, *S. pneumoniae*, HRV] during an AECOPD visit and also in the previous stable visit/in the previous visit
- Proportion of patients with sputum samples which are negative for specific pathogens [NTHi, Mcat, *S. pneumoniae*, HRV] during an AECOPD visit and also in the previous stable visit/in the previous visit

Conditional logistic regression models, stratified by patient, will be fitted to estimate the effect of the presence of bacterial/viral pathogens in sputum on the odds of experiencing an acute exacerbation rather than remain in a stable COPD state. Separate models considering bacteria detected by bacteriological culture and by PCR will be fitted. Both the impact of presence and new occurrence of each specific pathogen will be considered. New occurrence of a pathogen will be defined as the detection of the specific pathogen after negative sputum sample at previous [any/stable] visit. Seasonality will be taken into account as a dichotomous variable: high season (October to March) and low season (April to September). Study country will be also taken in consideration. Backward selection of variables will be adopted until all remaining variables have individual P values smaller than 0.10.

Complete models with interactions between NTHi, Mcat, *S. pneumoniae*, Rhinovirus and season will be also fitted.

The conditional logistic model allows estimating the impact of independent variables from observations from each individual patient. In other words, by stratifying by patient, there is no need to adjust for time-invariant covariates such as age and sex.

6.4.5. Microbiome analysis

Because *H. influenzae* species could not be differentiated from *H. haemolyticus* species based on culture data, these isolates will be further processed by PCR to confirm the presence of *H. influenzae*. Distribution of Hi versus Hh in positive culture samples will be reported. An attempt to differentiate NTHi from Hi will be also made.

Sputum samples positive for enterovirus will be further tested for quantifying human rhinovirus. Results for Enterovirus and QPCR rhinovirus will be reported.

6.4.6. Biomarkers

Descriptive statistics (N, mean, median, SD, minimum, maximum, first and third quartiles) for the level of each quantitative biomarker/haematology parameter will be tabulated for visit 1 and visit 3. The difference in sample mean will be reported together with a confidence interval.

Number and percentage of patients with fibrinogen, human serum C reactive protein (hsPCT), C-X-C Motif Chemokine Ligand 10 (CXCL10) values outside the laboratory normal ranges will be tabulated for visit 1 and visit 3.

Descriptive statistics will be presented overall and by GOLD grade at enrolment.

Changes in biomarkers will be evaluated according to the number of exacerbations occurred in the observation period using Pearson's correlation coefficient (or Spearman's rank-order correlation coefficient if the normal distribution assumption is not met).

6.5. Analysis of safety

The analysis of serious adverse events will be performed on the full analysis set.

Adverse events (AEs) and serious adverse events (SAEs) considered possibly related to the study participation and withdrawal due to AEs and SAEs during the entire study period will be described in detail.

7. ANALYSIS INTERPRETATION

All analyses are descriptive. The use of these descriptive analyses should be limited to supportive analysis of confirmatory analyses or hypothesis generation.

8. CONDUCT OF ANALYSES

8.1. Sequence of analyses

The analyses will be performed in two steps:

- An interim analysis will be performed when at least 40 AECOPD sputum samples are available. It will include all data available at the time of analysis. The rate of positive samples will be computed for Hi, NTHi and Mcat together and per pathogen. The analysis will be done based on as clean as possible data. No study report will be written at this stage.
- A final analysis of all objectives will be performed when data obtained up to planned last patient last visit are available. A final study report will be written at this stage.

Description	Analysis ID	Disclosure Purpose (CTRS=public posting, SR=study report, internal)	Dry run review needed (Y/N)	Study Headline Summary (SHS)requiring expedited communication to upper management (Yes/No)	Reference for TFL
Final analysis	E1_01	Study report	YES	NO	See TFL TOC
Interim analysis	E1_02	Internal	NO	NO	See TFL TOC

8.2. Statistical considerations for interim analyses

All analyses are descriptive and therefore no statistical adjustment for the interim analysis is required. No study report will be written for interim analysis.

9. CHANGES FROM PLANNED ANALYSES

Not applicable

10. LIST OF FINAL REPORT TABLES, LISTINGS AND FIGURES

The TFL TOC provides the list of tables/listings and figures needed for the study report. It also identifies the tables eligible for each analyses and their role (synopsis, in-text, post-text, SHS, CTRS,...). Note that all TFL aimed to be included as post-text are noted as post-text even if these are tabulation of individual data such as listing of SAE. The post-text material contain all source material for the study report and accordingly a post-text table may be redundant with an in-text table.

11.2. Data derivation

11.2.1. COPD severity stage

The baseline COPD severity stage will be derived by the investigator from the spirometry results at the screening visit. The spirometric classification of airflow limitation in COPD patients is based on post-bronchodilator FEV₁ and can be divided into four GOLD grades (mild, moderate, severe and very severe) [Global Initiative for Chronic Obstructive Lung Disease (GOLD). Global strategy for the diagnosis, management, and prevention of Chronic Obstructive Pulmonary Disease, updated 2013. Available from: http://www.goldcopd.org/uploads/users/files/GOLD_Report_2013_Feb20.pdf]. For the purpose of this study only patients with COPD graded from moderate to very severe will be enrolled.

Table 1 COPD severity stages included in the study

GOLD grade	In patients with FEV ₁ /FVC<0.70
Moderate	50% ≤ FEV ₁ < 80% predicted
Severe	30% ≤ FEV ₁ < 50% predicted
Very severe	FEV ₁ < 30% predicted

The resulting COPD severity variable will be used in all models in which COPD at baseline will be taken into account.

A four-grade refined assessment of COPD severity stages will be computed according to the newest GOLD criteria [GOLD, 2017 Global Initiative for Chronic Obstructive Lung Disease (GOLD). Global strategy for the diagnosis, management, and prevention of Chronic Obstructive Pulmonary Disease, updated 2017. Available from: <http://goldcopd.org/gold-2017-global-strategy-diagnosis-management-prevention-copd/>]. In the assessment scheme, patients should undergo spirometry to determine the severity of airflow limitation (i.e., spirometric grade). They should then undergo assessment of either dyspnea using mMRC or symptoms using CAT. Finally, their history of exacerbations (including prior hospitalizations) should be recorded.

For the purpose of this study we will only adopt CAT rather than adopting mMRC dyspnea scale. This choice is because the two tools are not interchangeable [Kim S, Oh J, Kim YI, Ban HJ, Kwon YS, Oh IJ, Kim KS, Kim YC, Lim SC. Differences in classification of COPD group using COPD assessment test (CAT) or modified Medical Research Council (mMRC) dyspnea scores: a cross-sectional analyses. *BMC Pulm Med.* 2013;13:35] and it is now recognized that COPD impacts patients beyond just dyspnea [Jones PW. Health status measurement in chronic obstructive pulmonary disease. *Thorax.* 2001; 56(11):880-7].

The four grades are:

- Patient Group A – Low Risk, Less Symptoms Typically GOLD 1 or GOLD 2 (Mild or Moderate airflow limitation); and 0-1 exacerbation per year and no hospitalization for exacerbation; and CAT score < 10;
- Patient Group B – Low Risk, More Symptoms Typically GOLD 1 or GOLD 2 (Mild or Moderate airflow limitation); and 0-1 exacerbation per year and no hospitalization for exacerbation; and CAT score ≥ 10 ;
- Patient Group C – High Risk, Less Symptoms Typically GOLD 3 or GOLD 4 (Severe or Very Severe airflow limitation); and ≥ 2 exacerbations per year or ≥ 1 with hospitalization for exacerbation; and CAT score < 10;
- Patient Group D – High Risk, More Symptoms Typically GOLD 3 or GOLD 4 (Severe or Very Severe airflow limitation); and ≥ 2 exacerbations per year or ≥ 1 with hospitalization for exacerbation; and CAT score ≥ 10 .

Spirometry results for GOLD classifications, number of exacerbations per year, and number of exacerbation requiring hospitalization will be taken from the screening visit (visit 0). CAT score will be derived from visit 1.

11.2.2. HRQOL

11.2.2.1. CAT

The CAT index will be derived as the sum of the ratings recorded for each of the eight individual items. Each of these items has 6 possible scores (0, 1, 2, 3, 4 or 5), leading to a range of 0 to 40 for CAT score.

No missing items are expected because the e-diary system prompts the patient to complete an item of CAT to proceed to the following one. Partial questionnaires will be excluded.

11.2.2.2. SGRQ-C

The SGRQ-C total score will be derived as the weighted sum of the forty individual items leading to a range of 0 to 100 as detailed in the reference manual [St George's Respiratory Questionnaire for COPD patients (SGRQ-C), version 1.3, 2016].

The SGRQ-C symptoms, activity and impacts component scores will be derived as the weighted sum of subset of items as detailed in the reference manual.

No missing missing items are expected because the e-diary system prompts the patient to complete an item of SGRQ-C to proceed to the following one. Partial questionnaires will be excluded.

11.2.3. Sputum Quality

The quality of sputum is defined as follow:

- < 10 squamous epithelial cells/field: sample of good quality
- 10-25 squamous epithelial cells/field with significant numbers of cells derived from the lower respiratory tractus (ciliary epithelial cells, bronchial cells, round cells): sample of moderate quality
- > 25 squamous epithelial cells/field: sample of bad quality

11.3. Handling missing data

Missing or non-evaluable measurements will not be replaced. The only exception is detailed below.

The number of exacerbations per year will be extrapolated for patients withdrawing from the study to provide an estimate of the number of exacerbations over the one year observation period. The number of exacerbations in a year will be calculated by multiplying the number of exacerbations experienced by the patient by 13 and dividing by the number of 4-week periods the patient was followed up [Stockley R.A., Chopra N, Rice L. Addition of salmeterol to existing treatment in patients with COPD: a 12 month study. *Thorax*. 2006;61:122-128].

$$\text{Number of exacerbations per year} = \frac{\text{Number of exacerbations} * 13}{\text{Number of 4-week observation period intervals}}$$

The calculation of exacerbation rate will be based on follow-up period intervals of four weeks to avoid obtaining high imputed rates if a patient withdrew very early from the study after experiencing an exacerbation. Four-week intervals will be adopted since treatment courses for moderate/severe exacerbations are <=2 - 4 weeks when appropriate.

11.3.1. Date derivation

Partial dates will not be considered as missing or not evaluable date. In case day is missing, 15th of month is used. In case day and month are missing, 30th of June is used.

Partial or missing initial and end dates for exacerbation will not be considered to measure the length of an exacerbation.

11.3.2. Missing data for electronic Diary Card alert

- Days with missing data will not be ignored when defining start of an e-diary signal: e.g., if a patient has two qualifying symptoms followed by a missing day, if the next day with data has two qualifying symptoms this will not be defined as an exacerbation. Hence, the start of an e-diary signal of an exacerbation will require 2 consecutive non-missing days of worsening. If there is partially recorded symptom data at a visit, however, only the observed values will be considered but the day will not be discarded.
- Days with missing data will be ignored when defining end of an e-diary signal of an exacerbation: e.g., if a patient has two days missing in the baseline period and one day missing in the 3- day moving average, both baseline and 3-day moving average values will be calculated using observed data only. Similar rules will apply when there is partially recorded symptom data at a visit (and daily average values will be calculated among the observed values).
- All available data will be used for each patient.
- As a general rule, the baseline symptom count score, and 3 day moving averages are calculated as the average count score of the observed days in the baseline period. For example, if an e-diary signal occurs from day 10 onwards, the baseline period will be the average between day1 and day2 (day1 being the first study day). If day 13 is missing, the 3 day moving average at day 14 will only take into account day 14 and day 15.
- If there are more than 2 consecutive days of missing data after an e-diary signal not resolved, the e-diary signal will not be considered resolved until the next day with observed data if the corresponding moving average is below the baseline value. In other words, if the 3-day average daily score is missing, the day will be counted in the duration of the episode.

11.4. Number of decimals

The following decimal description will be used for the analyses.

Parameters	Number of decimal digits
% of count, including LL & UL of CI	1
p-value	3
Mean, median	Number of decimals in the raw data + 1
SD	Number of decimals in the raw data + 2
Minimum, maximum, range	Number of decimals in the raw data
First and third quartiles	Number of decimals in the raw data + 1

LL = Lower Limit UL = Upper Limit CI = Confidence Interval

SD = Standard deviation

11.5. Methodology for computing CI

- All CI computed will be two-sided 95% CI.
- The exact 95% CIs for a proportion within a group will be calculated [Clopper 1934].

12. ANNEX 2: AECOPD DEFINITION AND CALCULATION RULE

12.1. Definition, onset, recovery, duration of an AECOPD event

AECOPD events are confirmed according to investigator judgment after an AECOPD visit which is aimed to exclude worsening in symptoms not related to an AECOPD event.

AECOPD visits are scheduled after an electronic Diary Card alert confirmed by the investigator (by phone call or at the study site) or after spontaneous site visits due to worsening symptoms without any alert.

Electronic Diary Card alerts refer to daily symptoms recorded the morning after (also called morning symptoms). Alerts are based on the Anthonisen criteria:

- Worsening of two or more of the following major symptoms for at least two consecutive days*.*.: dyspnea, sputum volume, sputum purulence (colour)

Or

- Worsening of any major symptom together with any of the following minor symptoms for at least two consecutive days*.*.: sore throat, colds (nasal discharge and/or nasal congestion), fever (oral temperature $\geq 37.5^{\circ}\text{C}$) without other cause, increased cough, increased wheeze.

* *The same two symptoms do not have to be present on both days as long as at least one major symptom is present on both days.*

AECOPD onset will be defined as the first day of the two consecutive days of worsening symptoms.

AECOPD recovery will be determined/confirmed by the investigator/delegate during (a) follow-up phone call(s) which will take place every 2 weeks until the AECOPD has resolved. The end date will be based on when the investigator/delegate determines that the AECOPD symptoms have resolved. In determining this end date, consideration will be given to symptoms recorded in the electronic Diary Card and patient assessment during the phone calls.

AECOPD duration will be defined as the number of days from AECOPD onset (included) and AECOPD recovery (not included).

Duration = date2 – date1 + 1,

with date2: AECOPD recovery date,

date1: AECOPD onset date

12.2. Recovery and duration of an exacerbation according to EXACT-PRO:

An EXACT-PRO AECOPD event is defined as a 12 point increase above baseline for 2 consecutive days, or a nine point increase for 3 consecutive days.

The baseline EXACT-PRO score is calculated as the average daily EXACT-PRO score over days 14 to 8 preceding AECOPD symptomatic onset.

AECOPD recovery according to EXACT-PRO corresponds to the day at which the EXACT-PRO score return to its baseline value (or below) [Mackay AJ, Donaldson GC, Patel AR, Singh R, Kowlessar B, Wedzicha JA. Detection and severity grading of COPD exacerbations using the exacerbations of chronic pulmonary disease tool (EXACT). *Eur Respir J*. 2014;43(3):735-44.].

The AECOPD duration according to EXACT-PRO will be defined as the number of days from AECOPD onset (included) and AECOPD recovery according to EXACT-PRO (not included).

12.2.1. EXACT-PRO baseline score at enrolment

An EXACT-PRO baseline score at enrolment will be computed as the mean within-patient score over 7 days, with data present for a minimum of 4 of the 7 days. If fewer than 4 days of data are available, the EXACT baseline score cannot be calculated.

12.3. Time between 2 e-diary signals for exacerbations/evaluation of baseline symptom score:

The minimum duration between 2 e-diary signals with distinct baseline value is 15 days, which is the minimal period for which a new full exacerbation-free baseline can be calculated for the next e-diary episode.

If a new worsening of symptoms occurs between 6 and 14 days after the end of a previous exacerbation, the baseline period used will be the same baseline as the one of the original exacerbation. Therefore, it will last until the daily symptom count score has gone below the baseline symptom score of the previous event.

12.4. Definition of Missed AECOPD visits

Missed AECOPD visits with medical records (dashed boxes 2 and 7 in Figure 1) will capture:

- an alert from the electronic Diary Card without a site visit but that cannot be discounted as a possible exacerbation signal after reconciliation (detailed in the Study Procedure Manual),

and/or

- an exacerbation reported retrospectively during a scheduled visit clinically documented for which there has not been a corresponding exacerbation visit.

Onset date, recovery date and severity will be retrieved by medical records.

For the analyses not involving the collection of any biological specimen, exacerbations will refer to AECOPD events plus missed AECOPD visits with medical records.

Missed AECOPD visits without medical records (dashed box 3 in Figure 1) will capture:

- an alert from the electronic Diary Card, assessed AECOPD during the phone call, without a site visit and without AECOPD medical records.

12.5. Unconfirmed AECOPD event with morning e-diary signal alert notification.

An alert from the electronic Diary Card not confirmed to be an AECOPD after contact by phone call or at the study site.

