 - For each AECOPD: AECOPD visit (within 96 hours of the onset of the symptoms) and follow-up phone call(s) (at least every 2 weeks until the AECOPD has resolved). Follow-up phone contacts will define end of AECOPD.
- **COPD symptoms**
Subjects will be asked to record their COPD symptoms in an electronic Diary Card on a daily basis:
 - Daily in the morning throughout the study: Morning symptoms questionnaire.
 - Daily at bedtime throughout the study: EXACT-PRO (EXAcerbations of Chronic Pulmonary Disease Tool - Patient Reported Outcome) questionnaire.
- **Biological samples:**
 - **Sputum samples** collected at site (spontaneous or induced, as per investigator judgement) will be collected at each study visit at the site (scheduled [stable] visits and AECOPD visits) if, in the opinion of the investigator, it is safe for the subject.

Or

- **Sputum sample collected at subject's home (spontaneous).** Self-collection of the sputum sample will be allowed in specific cases, where the first dose of antibiotics absolutely needs to be taken before an AECOPD visit can take place. This is not allowed at scheduled visits when subject should be in stable condition.

Note: The sputum samples collected during AECOPD should preferably be obtained before administration of the first dose of antibiotics to treat the AECOPD (if applicable).

- **Blood samples** for biomarker testing will be collected at Visit 1 (M0) and Visit 3 (M12).

- **HRQOL assessments**

- Subjects will be asked to complete the COPD assessment Test (*CAT*) at each study visit (scheduled [stable] visits and AECOPD visits).
- Subjects will be asked to complete the St. George's Respiratory Questionnaire for COPD patients (SGRQ-C) at each scheduled (stable) study visit (Visit 1 [Month 0], Visit 2 [Month 6] and at Visit 3 [Month 12]).
- Pre- and post-bronchodilator spirometry assessments will be done for all subjects at Screening Visit (pre-Month 0) and at Visit 3 (Month 12).

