3.3. Tertiary objectives

- To assess the use of EXACT-PRO for determining the end date of AECOPD.
- To evaluate the load of bacterial and viral pathogens in stable COPD and during AECOPD.
- To collect biological specimens for future respiratory disease-related testing:
 - Aliquots of sputum samples for assay development and microbiome analysis at stable visits and during exacerbation.
 - Blood sampling for potential biomarkers for identification/quantification of biomarkers at Visit 1 and Visit 3.

CONFIDENTIAL

201112 (EPI-NTHI-001 BOD APA)
 Statistical Analysis Plan Amendment 2 Final

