CAT and SGRQ-C (total score and symptoms, activity and impacts component scores) changes from first visit to final scheduled visit will be displayed according to the number of exacerbation occurred in the observation period. Correlation will be evaluated using Spearman's rank-order correlation coefficient.

Descriptive statistics (N, mean, median, SD, minimum, maximum, first and third quartiles) on the CAT score will be tabulated for any stable and any mild, moderate or severe exacerbation visit.

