6.4.5. Microbiome analysis

Further characterization of *H. influenzae*, *M. catarrhalis* and HRV strains will be performed. Details of the statistical analyses will be released in a separate additional analysis request.

CONFIDENTIAL201112 (EPI-NTHI-001 BOD APA)
Statistical Analysis Plan Amendment 2 Final**6.4.6. Biomarkers**

Descriptive statistics (N, mean, median, SD, minimum, maximum, first and third quartiles) for the level of each quantitative biomarker/haematology parameter will be tabulated for visit 1 and visit 3. The difference in sample mean will be reported together with a confidence interval.

Number and percentage of patients with fibrinogen, human serum C reactive protein (hsPCT), C-X-C Motif Chemokine Ligand 10 (CXCL10) values outside the laboratory normal ranges will be tabulated for visit 1 and visit 3.

Descriptive statistics will be presented overall and by GOLD grade at enrolment.

Changes in biomarkers will be evaluated according to the number of exacerbations occurred in the observation period using Pearson's correlation coefficient (or Spearman's rank-order correlation coefficient if the normal distribution assumption is not met).

The mean number of exacerbations per year overall, by severity of exacerbation and by presence of Hi and Mcat in the sputum collected at exacerbation visits will be calculated for patients with blood eosinophil levels $\geq 2\%$ and for those with blood eosinophil levels $< 2\%$ (the level measured for each patient at visit 1 will be used for this categorization).

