11.5. Methodology for computing CI

- All CI computed will be two-sided at 95% significant level.
- The exact 95% CIs for a proportion within a group will be calculated using Clopper Pearson method [[Clopper 1934](#)].

12. ANNEX 2: AECOPD DEFINITION AND CALCULATION RULE**12.1. Definition, onset, recovery, duration of an AECOPD event**

AECOPD events are confirmed according to investigator judgment after an AECOPD visit which is aimed to exclude worsening in symptoms not related to an AECOPD event.

AECOPD visits are scheduled after an electronic Diary Card alert confirmed by the investigator (by phone call or at the study site) or after spontaneous site visits due to worsening symptoms without any alert.

Electronic Diary Card alerts refer to daily symptoms recorded the morning after (also called morning symptoms). Alerts are based on the Anthonisen criteria:

- Worsening of two or more of the following major symptoms for at least two consecutive days*^{***}: dyspnea, sputum volume, sputum purulence (colour)

Or

- Worsening of any major symptom together with any of the following minor symptoms for at least two consecutive days*^{***}: sore throat, colds (nasal discharge and/or nasal congestion), fever (oral temperature $\geq 37.5^{\circ}\text{C}$) without other cause, increased cough, increased wheeze.

** The same two symptoms do not have to be present on both days as long as at least one major symptom is present on both days.*

CONFIDENTIAL

201112 (EPI-NTHI-001 BOD APA)
 Statistical Analysis Plan Amendment 2 Final

AECOPD onset will be defined as the first day of the two consecutive days of worsening symptoms.

AECOPD recovery will be determined/confirmed by the investigator/delegate during (a) follow-up phone call(s) which will take place every 2 weeks until the AECOPD has resolved. The end date will be based on when the investigator/delegate determines that the AECOPD symptoms have resolved. In determining this end date, consideration will be given to symptoms recorded in the electronic Diary Card and patient assessment during the phone calls.

AECOPD duration will be defined as the number of days from AECOPD onset (included) and AECOPD recovery (not included).

Duration = date2 – date1 + 1,

with date2: AECOPD recovery date,

date1: AECOPD onset date

12.2. Recovery and duration of an exacerbation according to EXACT-PRO:

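### Read literally, SAP 12.4's wording on any biological specimen leaves documented missed AECOPD visits out of the two blood-based analyses in 6.4.6 that count exacerbations

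*SAP*

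**What the plan says.** All references are to SAP Amendment 2 unless stated otherwise.

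- **12.4** defines missed AECOPD visits with medical records (boxes 2 and 7 of Figure 1) and then sets when they count: "For the analyses not involving the collection of any biological specimen, exacerbations will refer to AECOPD events plus missed AECOPD visits with medical records".
- **12.1** ties the narrower unit to a visit: "AECOPD events are confirmed according to investigator judgment after an AECOPD visit".
- **6.4.6** has two analyses of blood results that need an exacerbation count. The first reads "Changes in biomarkers will be evaluated according to the number of exacerbations occurred in the observation period". The second compares patients with Visit 1 eosinophils of at least 2% with those below 2%, and reports "The mean number of exacerbations per year overall, by severity of exacerbation and by presence of Hi and Mcat in the sputum". Neither says which count is meant.
- **3.3** places blood sampling under the objective "To collect biological specimens for future respiratory disease-related testing". Protocol Table 7 (section 6.5.2) also lists blood for biomarkers among the biological samples, with Visits 1 and 3 as its only time points.
- **6.3.6** says that CAT and SGRQ-C changes "will be displayed according to the number of exacerbation occurred in the observation period". No specimen is involved there.
- **6.3.4.1** defines confirmed exacerbations, for the incidence rates, as boxes 5 and 6 plus boxes 2 and 7.

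**The concern.** The condition in 12.4 makes sense for sputum taken at an exacerbation: with no AECOPD visit there is no such sputum. The word *any* carries it further. It also catches analyses whose only specimen is blood taken at scheduled visits, and their exacerbation count does not depend on sampling during an exacerbation.

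A programmer who applies 12.4 as written would give the 6.4.6 analyses boxes 5 and 6 only. The 6.3.6 analysis would get boxes 2, 5, 6 and 7 for the same patients, under almost identical wording. Documented exacerbations would then be missing from the eosinophil table's yearly means, and the biomarker correlation would rest on a partial count.

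The eosinophil table makes this more likely. It is new in Amendment 2, whereas the 12.4 sentence is unchanged since Version 1. One sentence in 6.4.6 also combines rows that need AECOPD sputum (Hi, Mcat) with rows that do not (overall, by severity), so a single restricted count for the whole table is a foreseeable choice.

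**Working it through.** The plan gives no figure on this point to reproduce. The check has two parts.

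**1. Which count each analysis gets under a literal reading**

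| Analysis | Specimen involved | When taken | Count under 12.4 |
|---|---|---|---|
| 6.3.6 CAT/SGRQ-C change vs number of exacerbations | none | – | boxes 2, 5, 6, 7 |
| 6.4.6 biomarker change vs number of exacerbations | blood | Visits 1 and 3 | not granted boxes 2 and 7; leaves 5 and 6 |
| 6.4.6 eosinophil table, overall and by severity | blood | Visit 1 | not granted boxes 2 and 7; leaves 5 and 6 |
| 6.4.6 eosinophil table, Hi and Mcat rows | blood and AECOPD sputum | Visit 1 and AECOPD visit | boxes 5 and 6, rightly |

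Only the last row needs a specimen from the exacerbation itself. The by-severity rows can be filled for missed visits too, because 12.4 takes their severity from the medical records.

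**2. Size, as a range**

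Inputs:
- m, the share of confirmed exacerbations that are missed visits with records. The documents do not give it; 5% to 40% is assumed.
- A true rate of 1 per patient-year, one of the scenarios in protocol Table 13.
- Overdispersion Φ of 1 and 2, also from Table 13. As a check that Φ is read as the protocol uses it: for T = n = 160 and Φ = 2, the half-width is 1.96 × √(2 × 160) / 160 = 0.219, which gives the table's 0.78 to 1.22.

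Formulas, with p = 1 − m and events missed at random:
- Observed mean = p × true mean.
- Correlation between the reduced and the full count = √[pΦ / (1 + p(Φ − 1))]. If missing is unrelated to the biomarker, a Pearson correlation with the count is multiplied by this factor.

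Example, m = 20%: mean 0.80; factor √0.8 = 0.894 for Φ = 1, and √(1.6/1.8) = 0.943 for Φ = 2.

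| m | Mean per year (true 1.00) | Factor, Φ = 1 | Factor, Φ = 2 |
|---|---|---|---|
| 5% | 0.95 | 0.975 | 0.987 |
| 10% | 0.90 | 0.949 | 0.973 |
| 20% | 0.80 | 0.894 | 0.943 |
| 30% | 0.70 | 0.837 | 0.907 |
| 40% | 0.60 | 0.775 | 0.866 |

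The ratio of means between eosinophil groups is biased only if m differs between them. With 20% missed in one group and 10% in the other, a true ratio of 1 becomes 0.80/0.90 = 0.89.

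**The case against.** The strongest reply is that 12.4 says what happens when no specimen is involved and does not say what happens otherwise. The restricted count is an implication. The sentence sits in a section on missed AECOPD visits, where the only specimen lost is sputum, so its author may have meant sputum alone. Section 6.4.6 says *exacerbations* rather than *AECOPD events*, and elsewhere (for example 6.3.5.1) the SAP keeps the two apart. Near-identical wording in 6.3.6 would ordinarily mean the same count.

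Much of this stands: the full count may well be what was intended. But *exacerbations* is exactly the term that 12.4 makes conditional on specimens, so using it in 6.4.6 does not settle the matter. Section 12.4 is not the only definition in the SAP, but the wider wording in 6.3.4 and 6.3.4.1 governs incidence rates. Where the authors wanted confirmed exacerbations elsewhere, as in the corticosteroid table of 6.3.8, they named them; 6.4.6 does not. The mock tables might show the choice, but they are in a separate document.

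The second reply is that the effect is small, and this is fair for the correlation. Protocol 9.2 implies about 160 completers (80% of 200). An assumed correlation of 0.28 then has a standard error of about (1 − 0.28²)/√159 = 0.07. At m = 20% and Φ = 1 it would fall to 0.28 × 0.894 = 0.25, a shift of 0.03. The shortfall in the yearly means is different: it is systematic, always downward, and does not shrink with sample size.

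**Conclusion.** Wrong as written, low impact. Section 12.4 is too broad: applied literally it denies two blood-based analyses the documented missed visits, for a reason that applies only to sputum from the exacerbation. Dropping those events can only lower the yearly mean, by the share m. It may also weaken the correlation; the factors above assume that missing is unrelated to the biomarker. The documents do not allow m to be estimated, so the range is illustrative.

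A reader might infer more than the documents support:

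- *That the SAP prescribes an incomplete count for biomarkers.* It does so only by implication.
- *That patients are left out.* They stay in; some of their exacerbations are not counted.
- *That severe exacerbations, or those treated elsewhere, are lost most.* This is plausible, since protocol 3.1.1 mentions hospitalisation and another physician as examples of why a patient cannot be reached. But no document gives the mix, and 12.4 also covers diary alerts that could not be discounted and documented events reported later. Any figure for a shortfall in the severe row would only restate an assumed loss rate.
- *That the biomarker section as a whole is affected.* The Visit 1 and Visit 3 summaries, the out-of-range counts and the tables by GOLD grade use no exacerbation count.

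Both affected analyses are tertiary, and SAP section 7 limits all analyses to descriptive, supportive or hypothesis-generating use.

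**What to change.** - In 12.4, replace the opening condition with: *for analyses not based on a specimen collected at the AECOPD visit*. The rest of the sentence can stay.
- In 6.4.6, state that the biomarker correlations and the overall and by-severity rows of the eosinophil table use confirmed exacerbations (boxes 2, 5, 6 and 7), and that only the Hi and Mcat rows are limited to AECOPD events with sputum.

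The same edit serves whether the present text is taken as an exclusion or as an ambiguity. It costs a few words in the SAP. No new data are needed, and the full count is already derived for 6.3.4.1.
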